## 7.7 Pemphigus Disease Area Index (PDAI)

Pemphigus severity and disease activity will be measured using the PDAI in regions where a validated questionnaire is available. A PDAI total activity score will be determined at screening. To be eligible for study participation, the patient's grade by disease severity must be  $>4$ . Assuming subject eligibility, the PDAI will be administered during Treatment Period and Follow-up Period. Disease severity categories by PDAI are mild (0 to 8), moderate (9 to 24), and severe ( $\geq 25$ ) ([Shimizu et al., 2014](#)). The Investigator will determine a PDAI score as follows: 0 to 250 points for disease activity ( $\leq 120$  for skin,  $\leq 10$  for scalp, and  $\leq 120$  for mucosa), and 0 to 13 points for damage ( $\leq 12$  for skin and  $\leq 1$  for scalp) ([Rosenbach et al., 2009](#)). See [Appendix 2](#).

## 7.8 Study Drug Administration

SYNT001 will be given as a 250-mL IV infusion over 1 hour  $\pm$  15 minutes using a 0.2-micron, inline filter.

## 7.9 Photographs

Photographs will be taken of active lesions and follow-up photographs will be taken of the same areas at timepoints indicated in [Table 2](#) and [Table 3](#). Subjects who begin a steroid taper will have additional photographs taken at the clinic visit during which the decision to begin the taper is made. A separate manual describing the procedures for taking photographs will be provided.

## 7.10 Health-Related Quality of Life Assessments

For Cohort 2, health-related quality of life will be assessed using ABQoL and Skindex-29 in regions where a validated questionnaire is available. The ABQoL questionnaire was developed

in Australia as a patient-based measure to quantify disease burden, monitor disease activity and evaluate response to therapeutic intervention in patients with autoimmune bullous disease (Sebaratnam et al., 2013; Sebaratnam et al., 2015) (Appendix 3). Skindex-29 was developed to measure the effects of skin disease on patients' quality of life using a self-administered 30-question dermatology survey (Chren et al., 1996) (Appendix 4).

## 7.11 Adverse Event Assessments

Information regarding the occurrence of AEs will be collected from the time the subject signs the informed consent form and continuing through the last study visit. Findings at screening and Day 0 (pre-dose) will be recorded as medical history. Any known untoward event that occurs beyond the AE reporting period that the Investigator assesses as related to study drug also should be reported as an AE. Clinical AEs will be graded using the NCI CTCAE, Version 4.03 (Appendix 1).

**Note:** AEs resulting in a subject's permanent discontinuation from the study, regardless of seriousness or relationship to study drug, MUST be promptly reported to the Sponsor. Additionally, subjects must be followed until return to normal and/or resolution of the AE.

See Section 10 for more information.

## 7.12 Prior and Concomitant Medications

All treatments a subject receives within 14 days prior to enrollment through the end of the study will be documented on the source document and eCRF. A history of treatments taken for the primary disease, even if not taken within the 14 days prior to enrollment, will be collected.

### Permitted Medications

Concomitant medication and treatment for co-existing conditions, including those for pemphigus, are permitted if not listed as prohibited.

1. Topical antibiotics to treat active infections that occur during the study.
2. Topical or systemic treatments for oral candidiasis.
3. Topical lidocaine for transient pain relief as needed.
4. Concomitant treatment that is medically indicated for any AEs the subject experiences during the study.
5. Medication for potential infusion-related reactions (IRRs) including post-infusion headache: The Investigator may recommend prophylactic use of acetaminophen, IV hydration, diphenhydramine, histamine2 (H2) blockers (eg, ranitidine, famotidine), etc to manage potential IRRs.
6. Low-strength corticosteroids (eg, hydrocortisone ≤1%) applied to a single lesion contributing <10% of the PDAI total activity score.
7. Topical tacrolimus, sirolimus or pimecrolimus applied to a single lesion contributing <10% of the PDAI total activity score.
8. Dexamethasone elixir solution for oral lesions if dose remains stable throughout trial participation (swish and spit only).

9. Stable regimen of the following systemic immunosuppressants: azathioprine, mycophenolate mofetil, methotrexate, dapson, cyclosporine, tacrolimus, sirolimus, corticosteroids, or low dose oral cyclophosphamide ( $\leq 100$  mg/day).

Fourteen days after the final dose of SYNT001, corticosteroids may be tapered at the Investigator's discretion.

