## 1. SYNOPSIS

Study title	A Phase 1b/2, Multicenter, Open-Label, Safety, and Dose-Finding Study of SYNT001 in Subjects with Pemphigus (Vulgaris or Foliaceus)
Sponsor	Syntimmune, Inc.
Protocol number	SYNT001-103
Clinical phase	Phase 1b/2
Number of study centers	Approximately 20 global study sites
Study rationale	
Pemphigus is a potentially life-threatening group of rare blistering autoimmune diseases that affect the skin and mucous membranes. The exact cause is unknown, though autoantibodies are thought to play an important pathogenic role in the mucosal and cutaneous manifestations in patients with pemphigus.
 
The prognosis of pemphigus has markedly improved over the last decades with steroid therapy. Nevertheless, mortality remains an issue (1.6% to 12% of cases) (Hsu et al., 2016; Kasperkiewicz et al., 2017; Langan et al., 2008). In these cases, death typically occurs as a consequence of treatment-related systemic infections and in a smaller proportion, as a consequence of superinfected lesions. While steroids have greatly improved patient outcomes, they are associated with serious and long-lasting side effects; therefore, their use should be limited as much as possible. Although other currently available treatments for certain autoimmune disorders, including immunosuppressants, intravenous immunoglobulin (IVIG), plasmapheresis, and anti-CD20 monoclonal antibodies (mAbs), such as rituximab, can be effective, they can be associated with significant adverse effects and delayed or non-durable responses.
 
SYNT001 targets key mechanisms contributing to pathology in a variety of immunoglobulin G (IgG)-mediated autoimmune disorders. When administered to healthy subjects, SYNT001 has been shown to significantly decrease total IgG, as well as immune complexes with which IgG is associated. Based on these results, it is predicted that SYNT001 will also reduce the levels of pathogenic autoantibodies. This could lead to a decrease in the mucosal and cutaneous manifestations in patients with pemphigus. Moreover, the ability of SYNT001 to reduce circulating immune complexes (CICs) and the associated innate and adaptive immune responses may allow for sustained disease modification. Thus, this study is being conducted to evaluate the safety and immunogenicity and determine a minimally effective dose (MED) of intravenous (IV) SYNT001 in pemphigus patients.

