## 2. BACKGROUND AND RATIONALE

SYNT001, a humanized, affinity-matured IgG4-kappa monoclonal antibody (mAb), blocks immunoglobulin G (IgG) and IgG immune complex (IC) interactions with the neonatal crystallizable fragment receptor (FcRn), and inhibits the varied roles of FcRn in the immune response.

Through specific and high affinity blockade of FcRn, SYNT001 has been shown to increase the catabolism of IgG and IgG IC in healthy volunteers and is predicted to block the ability of IgG IC to activate intracellular signaling events associated with binding to FcRn. This predicts that SYNT001 will also accelerate degradation of endogenous circulating IgG autoantibodies and IgG-IC specifically involved in the pathogenesis of autoimmunity. Blocking FcRn interactions with IgG ICs further predicts that SYNT001 will have consequences for innate and adaptive cellular immunity. In the first instance, blocking multimeric IgG IC interactions with FcRn within antigen-presenting cells should result in inhibition of IC-mediated inflammatory cytokine production and release by these cells. In addition, as FcRn determines the intracellular itinerary of IgG ICs within and among compartments important in cellular immunity, it is further anticipated that SYNT001 will block antigen processing and presentation of antigens contained within ICs that would otherwise lead to CD8+ and CD4+ T cell activation. Thus, SYNT001 is expected to specifically target immune functions associated with IgG and IC that are involved in certain IgG-mediated autoimmune conditions.

SYNT001 targets key mechanisms contributing to pathology in a variety of IgG-mediated autoimmune disorders.

While current treatments for certain autoimmune disorders, including chronic steroids, immunosuppressants, intravenous immunoglobulin (IVIG), plasmapheresis, and anti-CD20 mAbs, such as rituximab, can be effective, they are associated with significant adverse effects, and delayed or non-durable responses.

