### 6.3 Exclusion Criteria

A subject who meets any of the following criteria is ineligible for the study:

1. Subject unable or unwilling to comply with the protocol.
2. Active non-hematologic malignancy or history of non-hematologic malignancy in the 3 years prior to screening (exclusive of non-melanoma skin cancer and cervical cancer in situ).
3. Positive for human immunodeficiency virus (HIV) or hepatitis C antibody.
4. Positive for hepatitis B surface antigen.
5. Active infection or history of recurrent infections.
6. IVIG treatment within 30 days of screening.
7. Received any cytotoxic (other than azathioprine) or any non-anti-CD20 mAb therapy in the 3 months prior to screening.
8. Any exposure to an investigational drug or device within the 30 days prior to screening.
9. Plasmapheresis or immunoadsorption within 30 days of screening.
10. Cellular therapy, including chimeric antigen receptor and T-cell (CAR-T), at any time prior to screening.
11. Use of any systemic or topical immunosuppressive drugs within 3 months of screening not including dose allowed by the inclusion criteria.
12. Serum total IgG <600 mg/dL at screening.
13. Subject has any current medical condition that, in the opinion of the Investigator, may compromise their safety or compliance, preclude successful conduct of the study, or interfere with interpretation of the results (eg, a significant pre-existing illness or other major comorbidity that the Investigator considers may confound the interpretation of the study results).
14. Any vaccination within 2 weeks of screening.

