### **Prohibited Medications**

Use of the following medications will not be permitted during the study unless specified above as permitted:

1. Rituximab or other anti-CD20 antibody
2. Monoclonal antibodies other than study drug
3. Any topical or systemic immunosuppressive drugs apart from those that are listed as permitted.
4. IV corticosteroids prior to infusion (except in subjects who received corticosteroids for treatment of a prior IRR to SYNT001)
5. Any investigational drug or device
6. Vaccinations within 2 weeks of screening through 28 days following final dose of study drug

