## **9. STUDY RULES**

### **9.1 Subject Withdrawal**

Every reasonable effort will be made to keep the subject in the study; however, if a subject withdraws from the study, the Investigator should complete and report the reasons for withdrawal as thoroughly as possible. The reason(s) for termination must be clearly documented on the appropriate page of the eCRF.

Subjects who have received at least one SYNT001 dose and withdraw or prematurely discontinue study drug should be encouraged to attend, at a minimum, the early termination (ET) visit Day 112 (Cohort 1) or Day 91 (Cohort 2). Subjects in Cohort 2 will also be encouraged to attend the remaining follow up visits on Days 112 and 140.

If the subject fails to return for these assessments for unknown reasons, every effort (eg, telephone, email, and letter) should be made to contact them.

The reason(s) for a subject's participation in the study may be prematurely discontinued will be documented and include:

1. The subject wishes to withdraw from the study.
2. Request by a regulatory agency or Institutional Review Board).
3. The subject experiences a significant or intolerable AE.
4. The subject experiences a significant adverse change in vital signs, physical examination findings, or clinical laboratory parameter.
5. The subject has a need for a concomitant medication that is not permitted by the study protocol.
6. The subject experiences generalized impairment or mental incompetence that would result in the subject being unable to understand his or her participation in the study.
7. If, in the Investigator's medical judgment, further participation would be injurious to the health and well-being of the subject, or is not in the best interest of the subject.
8. Administrative reasons, such as subject non-compliance or a major protocol violation.

If at the discretion of the Investigator with consultation with the Medical Monitor, a subject requires a significant increase in dose(s) of anti-pemphigus medication(s) for the management of pemphigus, the subject should be encouraged to attend, at a minimum, the ET visit Day 112 (Cohort 1) or Day 91 (Cohort 2). Subjects in Cohort 2 will also be encouraged to attend the remaining follow up visits on Days 112 and 140.

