#### 9.5.3 Individual Stopping Rule

Dosing for any individual subject will be discontinued (ie, no further study drug will be given to that subject) if the subject experiences any study drug-related SAE or any study drug-related

non-serious AE that, in the judgement of the Investigator (following consultation with the Medical Monitor, if desired) or in the judgement of the Sponsor Medical Lead, suggest that it could be unsafe to administer further study drug to that subject.

Subjects who withdraw from this study due to an AE determined to be related to study drug are to be followed until there is:

- Resolution or stabilization of the AE determined to be related
- The subject is lost to follow-up
- The event is otherwise explained

If there is a persistent AE contributing to discontinuation that is determined to be related to SYNT001, subjects must be followed with appropriate medical management until resolution or stabilization. Refer to [Section 10](#) for more information.

Additionally, a subject will be discontinued from further treatment with study drug, at the discretion of the Investigator with consultation with the Medical Monitor, if they require a significant increase in doses of anti-pemphigus medications for the management of pemphigus.

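### The concomitant-treatment rule lets plasmapheresis, immunoadsorption and IVIG be given for pemphigus during Cohort 2 dosing without a protocol deviation

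*Protocol*

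**What the plan says.** The permitted-medication text in Section 7.12, repeated in the synopsis, reads: "Concomitant medication and treatment for co-existing conditions, including those for pemphigus, are permitted if not listed as prohibited". The prohibited list that follows has six items: anti-CD20 antibodies, other monoclonal antibodies, immunosuppressive drugs outside the permitted ones, IV corticosteroids before infusion, investigational products, and vaccinations. The nearest to the treatments at issue is item 3: "Any topical or systemic immunosuppressive drugs apart from those that are listed as permitted".

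Elsewhere the protocol deals with plasmapheresis, immunoadsorption and IVIG as follows:

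- **Rationale.** The synopsis lists current treatments as "immunosuppressants, intravenous immunoglobulin (IVIG), plasmapheresis, and anti-CD20 monoclonal antibodies (mAbs), such as rituximab", and Section 2 as "including chronic steroids, immunosuppressants, intravenous immunoglobulin (IVIG), plasmapheresis, and anti-CD20 mAbs, such as rituximab".
- **Eligibility (Section 6.3).** Criterion 6 is "IVIG treatment within 30 days of screening" and criterion 9 is "Plasmapheresis or immunoadsorption within 30 days of screening". Immunosuppressive drugs have a separate criterion, number 11.
- **Section 7.12, Corticosteroids.** Changes to pemphigus treatment beyond the steroid taper go to the Sponsor case by case. This sentence stands under the heading for the period that starts two weeks after the last dose.
- **Sections 9.5.3 and 9.1.** Study drug is stopped "at the discretion of the Investigator with consultation with the Medical Monitor, if they require a significant increase in doses of anti-pemphigus medications". Section 9.1 encourages an early termination visit when "a subject requires a significant increase in dose(s) of anti-pemphigus medication(s) for the management of pemphigus".
- **Section 10.3.3.** IVIG may be given to restore IgG if a bacterial infection occurs.

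**The concern.** Under a default of permitted unless prohibited, the prohibited list has to be complete for anything that acts on the endpoints. Here it leaves out the treatments that act on total IgG most directly.

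Section 3 bases dose selection on a total IgG nadir decrease of 60% to 90% and a PDAI activity reduction of at least 50%. The trial has no control group. By the protocol's own account, immunoadsorption can lower total IgG by up to 95% (Section 10.3.3) and has been linked to remission in pemphigus vulgaris (Section 2.2), while IVIG restores IgG immediately (Section 10.3.3). If one of these is given for a flare during dosing, that subject's IgG and PDAI no longer show what the SYNT001 regimen did. The site would still have followed Section 7.12 exactly.

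The gap is out of keeping with the care taken over weaker influences. Hydrocortisone of 1% or less is confined to a single lesion contributing under 10% of the PDAI activity score, and the corticosteroid dose may change by less than 10% until two weeks after dosing.

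**Working it through.** The plan gives no figure to reproduce, because Section 11.3 states that no formal sample size calculation was made. The check is a reading of the text followed by simple arithmetic.

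**Does any clause close the gap?**

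| Clause | Does it bar these treatments during dosing? |
|---|---|
| Prohibited item 3 | No. Apheresis is not a drug. The synopsis and Section 2 name IVIG and plasmapheresis beside immunosuppressants, and Section 6.3 gives them criteria separate from immunosuppressive drugs. |
| Exclusions 6 and 9 | No. They are entry criteria. Whether they also cover Day -14 to Day -1 can be read either way, so the gap is counted only from Day 0. |
| Sponsor consultation (7.12) | No. It applies only from two weeks after the last dose. |
| Sections 9.5.3 and 9.1 | No. They are discretionary, worded for dose increases, and govern further dosing and visits. |
| Withdrawal reason 5 (9.1) | No. It needs a medication that is not permitted, and these are permitted by default. |

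**Length of the window, Cohort 2.** The last dose is on Day 84 under both Table 3 and Table 10.

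- 84 + 14 = Day 98 (Day 95 to 101 with the ±3-day visit window).
- Share of maximum participation: 98/154 = 63.6%. The 154 days include up to 14 days of screening; from Day 0 the share is 98/140 = 70.0%.
- For a subject who stops dosing early, the 14 days run from the actual last dose.

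**Doses and visits inside the window.**

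- Table 3 doses: Days 0, 7, 14, 28, 42, 56, 70 and 84, so 8 of 8.
- Table 3 post-baseline IgG and PDAI visits: Days 7, 14, 28, 42, 56, 70, 84, 91, 112 and 140, which is 10. Eight fall by Day 98.
- Table 10 (weekly option) doses: weekly from Day 0 to Day 84, so 13 of 13.
- Table 10 post-baseline visits: 12 weekly visits on Days 7 to 84, plus Days 91, 112 and 140, which is 15. Thirteen fall by Day 98.

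**Effect on the IgG criterion.** Section 2.2 gives a modelled nadir reduction of about 78%, leaving 22% of baseline. If a fraction *f* of that remainder is removed, the total reduction is 1 − 0.22 × (1 − *f*).

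- The 90% ceiling is passed when *f* > 1 − 0.10/0.22 = 54.5%.
- *f* = 25% gives 83.5%; *f* = 50% gives 89.0%; *f* = 95% gives 98.9%.
- For a subject at a 50% reduction, the 60% floor is reached when *f* = 1 − 0.40/0.50 = 20%.

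Applying the 95% figure to IgG already lowered by SYNT001 is an assumption. Section 10.3.3 reports it as depletion of total IgG with immunoadsorption, not on top of FcRn blockade.

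**Effect on the PDAI proportion, 12 subjects.** One altered responder moves it by 1/12 = 8.3 percentage points, two by 2/12 = 16.7. With no such use the shift is 0.

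**The case against.** The best case on the other side is that control exists in practice. A subject who needs apheresis or IVIG for pemphigus is one whose disease needs escalation, which is what Sections 9.5.3 and 9.1 address. An Investigator who has consulted the Medical Monitor would have to choose to continue SYNT001, and withdrawal in the subject's best interest is also available. The specific permitted items show that stable background therapy was intended. The study is small and descriptive, and every treatment is recorded, so any such use would be visible by subject.

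This lowers the likely frequency but does not remove the fault. The provisions are discretionary, their wording fits apheresis poorly, and they do not make the treatment a deviation. Recording shows that a value was affected; it does not recover what the regimen alone would have done.

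Three narrower points stand:

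- IVIG given after the nadir has been sampled cannot raise a nadir already recorded. With the modelled nadir at Days 21 to 28, IVIG's direct effect on that measure has a window well short of 98 days. The full window still applies to PDAI.
- The 54.5% threshold and the 8.3-point shift are illustrations, not predictions.
- Permitted item 4 allows any treatment medically indicated for an adverse event, Section 10.2 counts exacerbation of a pre-existing condition as one, and the prohibited list gives way to what is permitted. That route could admit even listed drugs such as rituximab for a flare, so adding names to the list is not sufficient alone.

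**Conclusion.** The concern holds and should be fixed. As written, the rule allows plasmapheresis, immunoadsorption and IVIG for pemphigus in Cohort 2 at least from Day 0 to Day 98, across every dose and 8 of 10 post-baseline IgG and PDAI visits (13 of 15 on the weekly schedule). After Day 98 the text adds only Sponsor consultation. This is a conduct rule that is wrongly drawn, not an analysis detail that could be left to a SAP.

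The day count assumes a subject who completes dosing through Day 84. The effect on results depends on use, for which the protocol gives no frequency: it is nil if nobody is treated this way, and 8.3 percentage points of the PDAI proportion for each altered responder among 12. IVIG for bacterial infection under Section 10.3.3 is deliberate and is not criticised here.

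**What to change.** Add one item to the prohibited list in Section 7.12 and the synopsis:

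> Plasmapheresis, immunoadsorption, and IVIG given for pemphigus, from screening to at least 14 days after the final SYNT001 dose; after that, only following consultation with the Sponsor.

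Add two clauses. First, permitted item 4 does not override this item when the adverse event is a pemphigus flare; wording the clause for the whole prohibited list would also close the route for anti-CD20 antibodies. Second, IVIG for bacterial infection under Section 10.3.3 remains allowed.

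A subject who needs one of these treatments can still receive it, under withdrawal reason 5 in Section 9.1. How IgG and PDAI values after such treatment are analysed can stay with the SAP.

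The cost is a short text change in two places. No new data are needed, because Section 7.12 already requires all treatments to be recorded. The drawback is possibly a few more withdrawals.
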